5.0 Procedures Involved

This study will use feasibility randomized controlled efficacy trial design. This single-site trial will include up to 60 adults with self-reported fear of dogs, snakes, and/or spiders who will be randomly assigned via the REDCap Randomization Module using a 1:1 allocation ratio to receive 12 sessions of exposure therapy over the course of 3 months via standard telemental health (TMH; $n=15$) vs. Doxy.me VR ($n=15$), a telemedicine-based virtual reality clinic. Participants randomized to the Doxy.me group will be provided with Quest 2 VR headsets with the Doxy.me VR application pre-loaded to the device. This VR clinic is a standalone app currently available on Quest 2 headsets via

invite only. The app is designed for a therapist to meet with a client in a private, comfortable VR clinic office. To join each other in VR, the therapist selects a room code and provides that code to their client, who joins by entering that code into the app. While in the same VR room, the therapist and client can interact by speaking with each other in immersive VR. Therapists can also spawn a variety of small animals such as dogs, snakes, and spiders for use in treating specific phobias. Therapists can browse, select, maneuver, remove, and choose animations for the animals to exhibit once made visible to the client.

Therapy sessions will be audio recorded and 20% will be observed by the PI to assess treatment fidelity. Primary clinical outcomes (i.e., phobia severity as measured by the SMSF) will be assessed at baseline and 3-months post-baseline. Intervention targets will include presence—assessed weekly via patient-report— and working alliance—assessed at mid- and post-treatment via study therapist- and patient-report. Benchmarks for feasibility will include enrolling up to 60 patients during months 1-9 of the trial (i.e., 3/month), 70% patient retention at 3-month follow-up, 70% of weekly self-report collected, and $\geq 80\%$ treatment fidelity.

5.2 Please select the methods that will be employed in this study (select all that apply):

 Audio/Video Recording	 Psychophysiological Recording
 Behavioral Interventions	 Record Review - Educational
 Behavioral Observations and Experimentations	 Record Review - Employee

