8.0 Study Timelines

8.1 The study timeline with estimated visits and their accompanying durations can be viewed in Figure 2. Study Schema and Schedule of Events. Participants will participate in a ≤60-minute initial consent and baseline assessment visit (Visit 1). They will then participate in 12 ≤60-minute therapy sessions (Visits 2-13) and up to 6, ~30-minute homework assignments per week over 12 weeks. Participants will also participate in 20-minute mid- and post-treatment assessments, which will occur during Visits 7 and 13, respectively. In total, participants will spend approximately 38 hours over 13 study visits (i.e., Baseline + 12 Therapy Sessions) engaging in study procedures over the course of three months.

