12.3 N/A

13.0 Withdrawal of Subjects

13.1 Anticipated circumstances under which participants will be withdrawn from the research without their consent include the event that they:

1. Begin participating in ongoing mental health therapy from a non-study therapist
2. Have changes to psychotropic medication use
3. Begin to report active suicidal and/or homicidal intent or plan
4. Begin to report active auditory, visual, and/or tactile hallucinations
5. Begin to report the occurrence of photosensitive epilepsy or seizures
6. Moves out of the State of Florida during the study period

13.2 If subjects completely withdraw from the research, study staff will attempt to provide them with a referral to a therapist in their area. If subjects partially withdraw from the research, study staff will attempt to administer mid- and post-treatment assessments. Subjects will be given the option to completely withdraw from the study including withdrawing previously collected data.

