16.0 Data Management and Confidentiality

16.1 We will assess feasibility of the proposed trial methodology using the following benchmarks: 30 participants will be enrolled in months 1-9 of trial, 70% of participants will be retained at three-month follow-up, 70% of weekly self-report assessments will be completed, and we will reach 80% or greater treatment fidelity.

The small sample size prevents any conclusions about efficacy; however, Analysis of Covariance will be used to conduct a preliminary assessment of between-group differences in clinical outcomes while co-varying for pre-treatment scores. We also will conduct a preliminary examination of associations between study targets including therapeutic alliance and presence.

16.2 D.

We will use the following security measures to protect data sources:

1. Data collected during the trial will be securely stored in a HIPAA compliant USF REDCap database, including informed consent documents, questionnaire data, and session notes.
2. Consent forms and de-identified data will be downloaded and stored in a secure HIPAA compliant Box folder.
3. All research data exported from REDCap will include ID numbers only.
4. Audio recordings will be stored in a secure HIPAA compliant USF Box folder.
5. Only IRB-approved and trained study personnel will have access to the REDCap project and box folder.
6. Computers, programs, and box folders containing data will be password-protected to prohibit unauthorized access.
7. The codes that link the name of the participant and the study ID will be kept confidential in REDCap along with other identifiers including first name, last name, full date of birth, address, email address, and cell phone number.
8. We have obtained a Certificate of Confidentiality from the National Institutes of Health so that we cannot be forced to disclose information that may identify participants, even by a court subpoena, in any federal, state, or local civil, criminal, administrative, legislative, or other proceedings.

16.3 We will use the following quality assurance measures for subject recruitment, enrollment, enrollment targets, and for the validity and integrity of the data:

1. study staff will complete and maintain up-to-date CITI and GCP training

2. study staff will be trained and supervised weekly by the PI
3. Standard Operating Procedures (SOPs) and study checklists will be used to train study staff and ensure fidelity to the study protocol

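### Phobia severity is scheduled at baseline and 3 months although a Visit 7 assessment already exists, so participants lost before 3 months have no specified post-baseline severity score

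*Protocol*

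**What the plan says.** Section 5.0 states that phobia severity, the primary clinical outcome, "will be assessed at baseline and 3-months post-baseline". The next sentence gives the intervention targets other schedules: presence weekly, and working alliance "assessed at mid- and post-treatment via study therapist- and patient-report".

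Section 8.1 provides "20-minute mid- and post-treatment assessments, which will occur during Visits 7 and 13, respectively". Section 7.1 also refers to a mid-treatment assessment. Visits 2 to 13 are therapy sessions 1 to 12, so Visit 7 is session 6, the session whose completion earns a gift card under section 20.2.

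Section 16.1 says that "Analysis of Covariance will be used to conduct a preliminary assessment of between-group differences in clinical outcomes while co-varying for pre-treatment scores", and one feasibility benchmark is that "70% of participants will be retained at three-month follow-up".

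On withdrawal, section 13.2 says: "If subjects partially withdraw from the research, study staff will attempt to administer mid- and post-treatment assessments". It adds: "Subjects will be given the option to completely withdraw from the study including withdrawing previously collected data".

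Table 1 lists the measures without time points. Figure 2 (the schedule of events) and the separate Measures document are not shown. I take the severity measure abbreviated SMSF in section 5.0 to be the SMSP-A of Table 1, and the 3-month assessment to be the post-treatment assessment at Visit 13.

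**The concern.** The text distinguishes schedules by measure and gives phobia severity the sparsest one. An ANCOVA of the 3-month score needs that score. A participant without it has only a baseline value of the outcome, even after attending Visit 7 and completing a 20-minute assessment there.

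Loss need not be unrelated to response. Sections 9.3 and 13.1 remove participants who start outside therapy or change psychotropic medication, either of which could follow a poor response. Section 9.3 also lists no longer showing phobia symptoms as a ground for ineligibility after enrolment. Section 13.1 does not repeat that item, so its use during treatment is unclear. If response-related loss differs between VR and TMH, a comparison of completers is biased. A mid-treatment severity score would let the model account for the part of the loss that mid-treatment response explains. A score not collected at Visit 7 cannot be recovered later by any analysis plan.

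**Working it through.** The protocol states no power or precision calculation, so there is no figure of its own to reproduce.

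**1. Number affected.** At the 70% benchmark, 0.30 × 30 = 9 participants lack a 3-month score, or 0.30 × 60 = 18 at the enrolment ceiling. To obtain the 30 with post-treatment data sought in section 11.1 at 30% loss, 30 / 0.70 = 42.9, so 43 must be randomised and about 13 are lost.

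**2. How many a Visit 7 score could reach.** Assume a constant hazard over the 12 therapy visits, reaching 30% by Visit 13. The proportion gone before completing Visit 7, the sixth of the 12, is 1 − 0.70^(6/12) = 0.163. As a share of all dropouts this is 0.163 / 0.30 = 54%. The score would thus exist for somewhat under half of them. If loss is concentrated late, it would exist for most.

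**3. Bias.** The assumptions below are not in the documents. Correlations are baseline–mid 0.6, baseline–final 0.5 and mid–final 0.7. The true difference is −0.50 SD, half of it present at mid-treatment. Each arm loses 30%, and dropout depends on the mid-treatment score in one arm only. Large-sample simulation gives:

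| Log-odds slope per SD | Completer ANCOVA | Mid score for all dropouts | Mid score for half |
|---|---|---|---|
| 0.5 | about −0.55 | −0.50 | −0.53 |
| 1.0 | about −0.60 | −0.50 | −0.55 |
| 1.5 | about −0.64 | −0.50 | −0.56 |
| 1.0 in both arms | about −0.50 | −0.50 | −0.50 |

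The completer bias is thus about 0.05, 0.10 and 0.14 SD. It scales with the coefficient of the final score on the mid score given baseline, (r_mf − r_bm × r_bf) / (1 − r_bm²). This is 0.40 / 0.64 = 0.625 at mid–final 0.7 and 0.50 / 0.64 = 0.781 at 0.8, a ratio of 1.25. At 0.8 the biases become about 0.07, 0.12 and 0.17 SD. For slopes of 1.0 to 1.5, about 0.10 to 0.15 SD is a fair summary, and simulation with 15 per arm agrees.

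**4. Precision under random dropout.** Let ρ² be the squared partial correlation of mid and final scores given baseline. The large-sample variance ratio, new model to completer ANCOVA, is 1 − ρ² × (1 − n_final / n_mid).
- ρ² = 0.40² / (0.64 × 0.75) = 0.333 at mid–final 0.7, and 0.50² / 0.48 = 0.521 at 0.8.
- Mid score for all: 1 − 0.70 / 1.00 = 0.30, so variance falls by 10% and 16%.
- Mid score for half the dropouts: 1 − 0.70 / 0.85 = 0.176, so variance falls by 6% and 9%.

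**5. Scale.** With baseline–final correlation 0.5, the standard error of the arm difference is √(0.75 × 2 / 15) = 0.32 SD with 15 completers per arm, and √(0.75 × 2 / 10.5) = 0.38 SD if 15 are randomised per arm and 30% are lost. The bias in step 3 is under half a standard error.

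**The case against.** A reader might infer that every dropout is left without a post-baseline score. Section 13.2 does not support this: staff will attempt the post-treatment assessment after partial withdrawal, so some who stop therapy still supply the ANCOVA outcome. The gap concerns complete withdrawal and loss to follow-up. Those who also withdraw their data are beyond any fix.

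A reader might also infer that severity is measured at baseline and 3 months and nowhere else. Section 5.0 names those two times without excluding others. The mid- and post-treatment assessments have the same length, section 7.1 speaks of questionnaire and interview results at mid-treatment, and the content of the weekly assessment is not visible. The measure may already be given at Visit 7. The point is therefore limited to what the text specifies, and the fix allows for this.

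Third, session and homework anxiety ratings are post-baseline data that a missing-data model could use, and such a model may sit in an analysis plan that is not shown. This is fair, and the absence of missing-data methods is not the complaint. Those ratings are not the outcome measure, however, and no analysis plan can supply a severity score that was not collected.

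Fourth, larger biases of 0.17 to 0.22 SD arise if dropout runs in opposite directions in the two arms and falls entirely after Visit 7. Nothing in the protocol points to that pattern, so I do not rely on it.

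Finally, the stakes are limited. Section 2.2 says the trial is not powered for hypothesis testing, section 16.1 rules out efficacy conclusions, and the feasibility benchmarks are unaffected. This stands and sets the priority.

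**Conclusion.** The concern holds as a cheap, specific improvement to data collection; it is neither an error nor a contradiction. As section 5.0 is written, participants who withdraw completely or are lost before 3 months have no specified post-baseline severity score and fall outside the planned ANCOVA.

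The gain depends on the dropout mechanism. With about 30% loss and the assumed correlations (baseline–final 0.5, mid–final 0.7 to 0.8), one-arm dependence on mid-treatment response gives a bias of about 0.10 to 0.15 SD. A Visit 7 score removes it if all dropouts have one and roughly halves it if half leave earlier. Random dropout brings a variance reduction of about 6 to 16%. With the same mechanism in both arms there is no bias to remove. The bias results also assume that loss depends on the mid-treatment score itself; loss driven by later, unrecorded change would not be corrected. Priority is modest.

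**What to change.** - Add the SMSP-A to the existing Visit 7 assessment and state this in section 5.0. If Figure 2 already schedules it there, correct the sentence in section 5.0 to match.
- In section 16.1, estimate the 3-month arm difference from a repeated-measures model with baseline severity, arm, visit, arm by visit and baseline by visit, and an unstructured covariance. Include all randomised participants with any post-baseline severity score.
- Keep the ANCOVA as the completer analysis. With no missing scores the two give the same 3-month estimate.
- Report by arm how many participants were lost before and after Visit 7, since this shows how far the added score can help.

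The cost is a few extra minutes per participant at a visit that already takes place, plus a few lines of analysis text. It must be done before participants pass Visit 7.

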1.0 Study Summary

1.1

Study Title	Doxy.me VR vs. Telemental Health-Based Exposure Therapy
Study Design	Feasibility randomized controlled efficacy trial
Primary Objective/Purpose	Assess the feasibility of conducting a randomized controlled efficacy trial comparing the delivery of exposure therapy via a telemedicine-based virtual reality clinic (Doxy.me VR) vs. standard telemental health (TMH) to adults with intense fear of dogs, snakes, and/or spiders.
Secondary Objective(s)/Purposes	Preliminarily examine the efficacy of using Doxy.me VR vs. TMH in reducing phobia severity.
Research Intervention(s)	Exposure Therapy
ClinicalTrials.gov NCT #	Registration on clinicaltrials.gov is pending
Study Population	Adults (≥ 18 years old) with intense fear of dogs, snakes, and/or spiders.
Sample Size	30
Study Duration for individual subjects	In total, participants will spend approximately 38 hours over 13 study visits (12 Therapy and 1 Baseline Assessment) engaging in study procedures over the course of three months.
Study Specific Abbreviations/ Definitions	telemedicine-based virtual reality clinic (Doxy.me VR); standard telemental health (TMH); Virtual Reality (VR); Cognitive Behavioral Therapy (CBT)

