2.0 Objectives

2.1 Primary Objective: Assess the feasibility of conducting a randomized controlled efficacy trial comparing the delivery of exposure therapy via a telemedicine-based virtual reality clinic (Doxy.me VR) vs. standard telemental health (TMH) to adults with intense fear of dogs, snakes, and/or spiders.

Secondary Objective: Preliminarily examine the efficacy of using Doxy.me VR vs. TMH in reducing phobia severity.

2.2 This is a feasibility trial and not powered for hypothesis testing.

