9.4 N/A

10.0 Vulnerable Populations

10.1 N/A

11.0 Local Number of Subjects

11.1 We aim to complete treatment with and obtain post-treatment assessment data from a total of 30 participants (15 in TMH and 15 in VR group). We will enroll up to 60 participants in the trial as needed to account for screen fails, withdrawals, and drops.

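### The enrolment benchmark for the primary feasibility objective is wrong as written: up to 60 at 3 per month in section 5.0, but 30 over the same months in section 16.1

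*Protocol*

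**What the plan says.** Protocol section 2.0 makes feasibility the primary aim: "Primary Objective: Assess the feasibility of conducting a randomized controlled efficacy trial". Sections 5.0 and 16.1 each list the same four benchmarks for it: enrolment, retention, completion of weekly self-report, and treatment fidelity.

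The enrolment benchmark appears twice, for the same nine months:

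- Section 5.0: "enrolling up to 60 patients during months 1-9 of the trial (i.e., 3/month").
- Section 16.1: "30 participants will be enrolled in months 1-9 of trial".

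Three other places bear on it:

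- The study summary (section 1.0) gives "Sample Size 30".
- Section 11.1 gives a completer target, "We aim to complete treatment with and obtain post-treatment assessment data from a total of 30 participants (15 in TMH and 15 in VR group"), and then a ceiling: "We will enroll up to 60 participants in the trial as needed to account for screen fails, withdrawals, and drops".
- The opening paragraph of section 5.0 says that up to 60 adults will be randomly assigned 1:1, and gives n=15 for each arm.

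The retention benchmark in section 16.1 is that "70% of participants will be retained at three-month follow-up".

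**The concern.** Two statements of one benchmark differ by a factor of two, and the larger is equated with a monthly rate that does not produce it. The larger figure is also worded as an upper limit, which sets nothing to be reached.

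The trial is expressly not powered for hypothesis testing, so the feasibility benchmarks are what its primary objective will be judged on. If the enrolment benchmark has no single value and no defined unit, the same recruitment result can be reported as having met it or missed it, depending on which section is cited. That choice could be made after the count is known.

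**Working it through.** **Inputs.** Nine months and 3 per month (section 5.0); up to 60 (sections 5.0 and 11.1); 30 enrolled (section 16.1); 30 with post-treatment data (section 11.1); 70% retention (sections 5.0 and 16.1); n=15 per arm (section 5.0).

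**Step 1: does the rate in section 5.0 reproduce its count?** Count = rate × months = 3 × 9 = 27. It does not give 60. In the other direction, 60 / 9 = 6.67 per month, and 6.67 / 3 = 2.2 times the stated rate. At 3 per month, 60 would take 60 / 3 = 20 months.

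**Step 2: does the rate fit section 16.1?** 30 / 9 = 3.33 per month, which rounds to 3. So 3 per month is compatible with 30 as a rounded rate, though not as an exact one (27 against 30; at exactly 3 per month, 30 takes 10 months). It cannot be a rounding of 6.67, which rounds to 7.

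**Step 3: what would meet or miss each statement?**

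| Statement | Enrolled in months 1–9 that satisfies it |
|---|---|
| Section 5.0, up to 60, read as worded (a ceiling) | any number from 0 to 60 |
| Section 5.0, 3 per month, read exactly | 27 or more |
| Section 16.1 | 30 or more |

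A count below 30 misses section 16.1 but does not breach the ceiling in section 5.0. A count of 27 to 29 also satisfies an exact 3 per month.

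**Step 4: what is being counted?** Section 11.1 includes screen failures among the 60 enrolled. Under Consent and Baseline Assessment in section 5.0, consent comes before the diagnostic interview, the final eligibility decision and randomisation, so a person who fails screening at that visit is not randomised. Yet the opening of section 5.0 has up to 60 adults randomised. The arm sizes in that same sentence give 15 + 15 = 30, not 60. The two sections therefore use 60 for different populations.

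**Step 5: how does the benchmark sit with the completer target?** Here I assume that the 70% applies to randomised participants and that being retained means giving post-treatment data.

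- 30 randomised: 30 × 0.70 = 21 with post-treatment data.
- To reach 30 with post-treatment data: 30 / 0.70 = 42.9, so 43 randomised, or 43 / 9 = 4.8 per month.

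Forty-three is within the cap of 60, but it is neither the 30 in section 16.1 nor the 27 implied by 3 per month.

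**The case against.** The best defence is that the protocol largely shows what each figure is for. Section 11.1 presents 60 as an allowance for losses. The study summary, the arm sizes and section 16.1, which says how feasibility will be assessed, all point to 30. On that reading the target is 30, the cap is 60, 3 per month is a rounded 3.33, and the cap has simply been put into one benchmark sentence by mistake.

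Much of this stands. It is the most natural reading, and it limits the harm. It does not remove the error: no section says which count governs, section 5.0 still names a cap as a benchmark and equates it with a rate that cannot produce it, and the unit remains unsettled.

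The same defence rules out some stronger readings that a reader might infer:

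- *Three rival targets of 27, 30 and 60.* The figure 27 is printed nowhere; it is 3 × 9, and the gap to 30 can be rounding. The material conflict is 60 against 30, and 60 against 3 per month.
- *A shortfall measured against 60.* If 60 is a ceiling, falling below it is not a failure, so it should not also be used as a target for scoring recruitment.
- *The benchmark counts consented people.* Section 11.1 suggests this, but section 5.0 speaks of up to 60 people randomised. The documents show an inconsistent unit and do not establish which one is meant.
- *A formal rule for proceeding to a full trial is compromised.* The protocol calls these benchmarks and states no progression rule.

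**Conclusion.** Wrong as written. Section 5.0 and section 16.1 give incompatible enrolment benchmarks for the same nine months (up to 60 against 30), and the count in section 5.0 needs 6.67 per month, 2.2 times the 3 per month beside it. As a ceiling, the section 5.0 figure cannot be failed, and the unit differs between sections 5.0 and 11.1.

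This conclusion rests only on the current protocol text and simple division; it needs no assumption about screen-failure rates. The figures of 21 and 43 do depend on how the 70% is applied, as stated in the working. They bear on the choice of number, not on whether the contradiction exists. Allocation, safety and the exploratory analysis of covariance are not affected.

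**What to change.** Use one enrolment benchmark, worded identically in sections 5.0 and 16.1:

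- **A minimum count.** For example, at least 30 participants in months 1–9.
- **Its matching rate** in place of the present parenthesis: 30 / 9, about 3.3 per month. The count should govern, because 3.3 × 9 = 29.7 falls just short of 30.
- **A defined unit:** consented or randomised. Either can be defended; the sponsor should choose one and say so.

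Keep 60 only as the cap in section 11.1, say there whom it counts, and bring the opening of section 5.0 (up to 60 randomised, 15 per arm) into line with it.

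When setting the number, decide whether it is meant to deliver the 30 completers of section 11.1. If it is, the protocol's own retention benchmark implies about 43 randomised (4.8 per month). If 30 is kept, the protocol should acknowledge that about 21 with post-treatment data is what its benchmarks would give.

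The cost is a wording amendment to the sections named. The benchmark may look slightly less favourable once it has a floor and a fixed unit.
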